5. TEST ARTICLE ALLOCATION AND MASKING

5.1. Test Article Allocation

The study lenses will be worn in a bilateral and random fashion using a 2x3 crossover design. A computer-generated randomization scheme will be used to randomly assign subjects, in blocks of 2, to one of the two lens wear sequences: Test/DT1MF/DT1MF or DT1MF/Test/Test. The randomization scheme will be stratified by site. The random scheme will be generated using the PROC PLAN procedure from Statistical Analysis System (SAS) Software Version 9.4 or higher (SAS Institute, Cary, NC).¹⁵

The study site must follow the randomization scheme provided and complete enrollment per the randomization list and not pre-select or assign subjects. Randomization will be performed at visit first visit prior to the first fitting. The following must have occurred prior to randomization:

- Informed consent must have been obtained.
- The subject must have met all eligibility criteria.
- The subject's screening and baseline information must have been collected.

When dispensing test articles, the following steps should be followed to maintain randomization codes:

- 1. Investigator or designee (documented on the Delegation Log) will consult the lens fitting schedule to obtain the test article assignment for that subject prior to dispensing.
- 2. Investigator or designee will record the subject's number on the appropriate line of the lens fitting schedule.
- 3. Investigator or designee will pull the appropriate test articles from the study supply. All test articles that are opened, whether dispensed (placed/fit on eye or dispensed outside the clinical site) or not, must be recorded on the Test Article Accountability Log in the "Dispensed" section.

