Sample size estimates for each co-primary and secondary endpoint were carried out separately using an approximation of the power of an F-test derived from the non-centrality parameter calculated from the observed F statistic of a linear model. Each endpoint was analyzed individually using a generalized linear mixed model with a multinomial distribution and the cumulative logit as the link function. Sequence of lens wear, period, lens and first order carryover effect were included in the model as fixed effects. Study nested within site was included as a random effect (G-side). Errors between measurements within the same subject across periods was model using a variance component (VC) covariance structure. The Kenward and Roger method was used for the calculation of the denominator degrees of freedom.¹⁶

To estimate the sample size for each co-primary and secondary endpoints, the odds ratio and the cumulative log-odds from the model described above for each endpoint was used to create a new dataset with the same structure and design as the historical studies. This new dataset was then analyzed using a generalized linear model with a multinomial distribution and the cumulative logit as the link function. Lens type was included as the only fixed effect; errors between measurements within the same subject across periods was model using a variance component (VC) covariance structure. The Kenward and Roger method was used for the calculation of the denominator degrees of freedom. The statistical power of each endpoint was calculated using the F-statistics as Power=P(F[Fcrit, v, ncp] > Fcrit); where Fcrit is the critical value of the central F distribution (Fcrit= $F_{[numdf,dmdf,0,alpha]}$) under Ho (Ho: centrality param = 0), v is the magnitude of the departure from Ho and ncp is the non-centrality parameter (Stroup).¹⁷

Table 8 displays the sample size estimates and associated power by endpoint. As indicated below, co-primary endpoints were powered \sim 92% individually yielding a combined power of \sim 85%. With respect to secondary endpoints, each hypothesis was also powered to at least \sim 96% power provided a combine power of \sim 93%. Therefore, the overall combined study power for co-primary and secondary hypotheses is 79.2% and is considered reasonable to support any conclusions from these analyses.

Table 8: Sample Size Estimates by Endpoint

Endpoint			# of Subjects	
Type	Item	Alpha	Complete	Power (%)

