14.5. Primary Analysis

The primary analyses will be conducted on the intent-to-treat population.

Clarity of Vision in Dim or Low Lighting and Clarity of Vision when Reading in Dim light Subjective responses for co-primary endpoint will be the outcome (*aval*) defined as category one if a subject responds' 'Excellent' or 'Very Good', the outcome is defined as category two

if a subject responds' 'Good' and the outcome is defined as category three if a subject responds' 'Fair' or 'Poor'.

Since both co-primary endpoints assess various aspects of vision in dim or low light, the association between the two endpoints will be assessed using a Cochran-Mantel-Haenszel chi-square test using the Frequency PROCEDURE in SAS 9.4. If the association between the co-primary endpoints is statistically significant at an alpha=0.05 then the following analysis methods will be implemented:

Primary Analysis Plan A (If associate between co-primary endpoints is significant)

The outcomes for co-primary endpoints will be analyzed together using a hierarchical generalized linear mixed model (GLMM) with a multinomial distribution and the cumulative logit as the link function. Sequence of lens wear, period, lens type, first order carryover effect, item and the interaction between lens by item will be included as fixed effects. Site and subject nested within site will be included as random effects. Residual errors between measurements within the same subject and period across items will be modeled using an unstructured covariance (UN) structure. If this structure fails to converge then a variance component (VC) structure will be used. The Kenward and Roger method will be used for the calculation of the denominator degrees of freedom.¹⁶

Comparisons between the Test and DT1MF will be carried separately for each item out using 2-sided 95% confidence intervals (CIs) constructed for the odds ratio (Test over DT1MF). Superiority will be concluded if a lower limit of a 95% CI is above 1.

The Model:

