Let $aval_{ijkl} = (aval1_{ijklm}, aval2_{ijklm}, aval3_{ijklm})$ denote the rating for l^{th} subject at the m^{th} site assigned to the k^{th} sequence for the i^{th} study lens during the j^{th} study period (i=1, 2; j=1, 2, 3; k=1,2; l=1.... n_m ; m=1,...,10). As previously described possible values of $aval_{ijklm}$ are $aval_{ijklm}$ =1 if a subject responds: 'Excellent' or 'Very Good', $aval_{ijklm}$ =2 if a subject responds: 'Good' and $aval_{ijklm}$ =3 if a subject responds: 'Fair' or 'Poor'. The Likelihood will be constructed as follows:

$$\begin{aligned} aval_{ijklm} \sim & \text{Multinomial } (p1_{ijklm}, p2_{ijklm}, p3_{ijklm}) \\ & p1_{ijklm} = aval1_{ijklm} \\ & p2_{ijklm} = aval2_{ijklm} - aval1_{ijklm} \\ & p3_{ijklm} = 1 - \sum_{X=1,2} pX_{ijklm} \end{aligned}$$

$$\text{Logit} \left(avalX_{ijklm} \right) = \beta_o + \beta_1 * sequence_k + \beta_2 * period1_j + \beta_3 * period2_j + \beta_4 * \\ lens_{i[j,k]} + \beta_5 * carry_{i[j,k]} + \beta_6 * item_h + \beta_7 * item_h * lens_{i[j,k]} + \delta_m + \gamma_{lm} + \varepsilon_{hijklm}$$

Where, β_0 is the intercept for X=1,2,3; $sequence_k=1$ if Test/DT1MF/DT1MF and $sequence_k=0$ if DT1MF/Test/Test; $period1_j=1$ if first period and $period1_j=0$ otherwise;

; $period2_j=1$ if second period and $period2_j=0$ otherwise; $lens_{i[j,k]}=1$ if Test and $lens_{i[j,k]}=0$ if DT1MF. $carry_{i[j,k]}=1$ if lens is Test and $carry_{i[j,k]}=0$ if lens is DT1MF.

Primary Analysis Plan B (If associate between co-primary endpoints is NOT significant)

The outcome will be analyzed separately for each primary endpoint using a generalized linear mixed model with a multinomial distribution and the cumulative logit as the link function. In each model, sequence of lens wear, period, lens type and first order carryover effect will be included as fixed effects. Site will be included as a random effect. Residual errors between measurements within the same subject across study periods will be modeled using an unstructured covariance (UN) structure. Comparisons between the Test and DT1MF will be carried out using 2-sided 95% confidence intervals (CIs) constructed for the odds ratio (Test over DT1MF). Superiority will be concluded if a lower limit of a 95% CI is above 1.

The Model:

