Let $aval_{ijkl} = (aval1_{ijklm}, aval2_{ijklm}, aval3_{ijklm})$ denote the rating for l^{th} subject at the m^{th} site assigned to the k^{th} sequence for the i^{th} study lens during the j^{th} study period (i=1, 2; j=1, 2, 3; k=1,2; l=1.... n_m ; m=1,...,10). As previously described possible values of $aval_{ijklm}$ are $aval_{ijklm}=1$ if a subject responds: 'Excellent' or 'Very Good', $aval_{ijklm}=2$ if a subject responds: 'Good' and $aval_{ijklm}=3$ if a subject responds: 'Fair' or 'Poor'. The Likelihood will be constructed as follows:

$$aval_{ijklm} \sim \text{Multinomial } (p1_{ijklm}, p2_{ijklm}, p3_{ijklm})$$

$$p1_{ijklm} = aval1_{ijklm}$$

$$p2_{ijklm} = aval2_{ijklm} - aval1_{ijklm}$$

$$p3_{ijklm} = 1 - \sum_{X=1,2} pX_{ijklm}$$

$$\text{Logit } (avalX_{ijklm}) = \beta_o + \beta_1 * sequence_k + \beta_2 * period1_j + \beta_3 * period2_j + \beta_4 * lens_{i[j,k]} + \beta_5 * carry_{i[j,k]} + \delta_m + \varepsilon_{ijklm}$$

Where, β_o is the intercept for X=1,2,3; $sequence_k=1$ if Test/DT1MF/DT1MF and $sequence_k=0$ if DT1MF/Test/Test; $period1_j=1$ if first period and $period1_j=0$ otherwise; $period2_j=1$ if second period and $period2_j=0$ otherwise; $lens_{i[j,k]}=1$ if Test and $lens_{i[j,k]}=0$ if DT1MF. $carry_{i[j,k]}=1$ if lens is Test and $carry_{i[j,k]}=0$ if lens is DT1MF.

Hypothesis Testing

Regardless of which Plan (Primary Analysis Plan A or B) is implemented, superiority testing will be conducted separately for each co-primary endpoint as follows:

Ho: $OR \le 1$ Ha: OR > 1

CR-6479, v 3.0

Where, the OR represents the odds of having a more positive experience (Excellent or Very Good) while wearing Test compared to DT1MF. Superiority of Test relative to DT1MF will be concluded if a lower limit of a 95% CI is above 1.

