14.6. Secondary Analysis

Clarity of intermediate and near vision will be analyzed using the intent-to-treat population while clarity of distance vision will be analyzed using the per-protocol population.

Clarity of Distance Vision

Subjective responses to this item (defined as *aval*) will be categorized in the same manner as described for the primary endpoints. The outcome will be analyzed and using the model described for Primary Analysis Plan B above.

Hypothesis Testing

Non-inferiority of the Test compared to DT1MF will be conducted as follows:

Ho: $OR \le 0.67$ Ha: OR > 0.67

Where, the OR represents the odds of having a more positive experience (Excellent or Very Good) while wearing Test compared to DT1MF. Non-inferiority of Test relative to DT1MF will be concluded if the lower limit of the simultaneous 95% CI (98.33% individually) is above 0.67. A cumulative odds ratio margin of 0.67 was utilized as this corresponds to nomore than a 10% difference using a reference rate of 0.58 for DT1MF.

Clarity of Intermediate and Near Vision

Subjective responses to these two items (defined as *aval*) will be categorized in the same manner as described for the primary endpoints. Association between these two endpoints will be assessed using the same test as the primary endpoints and will following the same strategy.

Hypothesis Testing

Regardless of which Plan (Primary Analysis Plan A or B) is implemented, superiority testing will be conducted separately for clarity of intermediate and near vision as follows:

Ho: $OR \le 1$ Ha: OR > 1

Where, the OR represents the odds of having a more positive experience (Excellent or Very Good) while wearing Test compared to DT1MF. Superiority of Test relative to DT1MF will be concluded if a lower limit of a simultaneous 95% CI (98.33% individually) is above 1.

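### Plan B, the only model for the distance non-inferiority test, links a subject's three ratings solely through a residual covariance that cannot be estimated as written, with no subject effect and no fallback

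*Combined protocol and SAP*

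**What the plan says.** Section 14.6 sends the distance item to one model, without the Plan A/Plan B choice that the other items have: "The outcome will be analyzed and using the model described for Primary Analysis Plan B above". The test compares the lower limit of a 98.33% interval for the odds ratio with 0.67, in the per-protocol population.

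Plan B in section 14.5 is a cumulative-logit model for three ordered categories with sequence, period, lens and carryover as fixed effects. On the random side it says: "Site will be included as a random effect. Residual errors between measurements within the same subject across study periods will be modeled" with an unstructured (UN) matrix. Its equation agrees: after the fixed effects come a site term and an error term inside the logit, and no subject term.

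Plan A differs in two ways. It has a subject effect: "Site and subject nested within site will be included as random effects". It also has a contingency: "If this structure fails to converge then a variance component (VC) structure will be used". Plan A's residual matrix runs across items within the same subject and period, whereas Plan B's runs across periods. Plan B states no contingency.

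For the planning model, section 14.2 says: "Errors between measurements within the same subject across periods was model using a variance component (VC) covariance structure". It lists no subject effect. Section 14.1 leaves further detail to a stand-alone SAP, which is not in the supplied text.

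**The concern.** With sequences "Test/DT1MF/DT1MF or DT1MF/Test/Test", each subject rates each item three times and wears both lenses. With sequence and period in the model, the lens effect is a within-subject contrast. Section 4.2 justifies the crossover on this ground. The gain reaches the confidence interval only if the fitted model knows which ratings share a subject.

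In Plan B only the UN residual carries that information, and a multinomial model has no free residual variance because the category probabilities fix it. Someone programming the text literally must either let the software settle an undetermined scale, which moves the odds ratio compared with 0.67, or abandon the matrix. After abandoning it, only site remains.

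Section 2.3 requires every primary and secondary hypothesis to be met, so a missed distance result alone fails the study objective and blocks the exploratory tests.

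**Working it through.** **Inputs from the documents.** Planning OR 1.27 (95% CI 0.82–1.98, Table 7); margin 0.67 and reference rate 0.58 (section 14.6); two-sided alpha 0.0167; N=83 with 99% power for distance (Table 8); 110 completers. Table 6 counts 64+66=130 per-protocol subjects among 75+78=153 completers. At that ratio the per-protocol set here would be 110×130/153≈93, so N=83 and N=110 bracket it.

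**Assumed, not in the documents.** Within-subject correlation 0.3, 0.5 or 0.7; the remaining 0.42 split as 0.27 Good and 0.15 Fair/Poor; no site variance.

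**1. The plan's own figures.** The margin reproduces. The odds at 0.58 are 0.58/0.42=1.381; 1.381×0.67=0.925; 0.925/1.925=0.481, a drop of 9.9 points. The 99% power does not reproduce. It needs SE = ln(1.27/0.67)/(2.393+2.326) = 0.6395/4.719 = 0.136. The Table 7 interval gives SE = ln(1.98/0.82)/3.92 = 0.225 on 153 subjects, or 0.225×√(153/83)=0.305 at N=83, hence power Φ(0.6395/0.305−2.393)≈38%. The cumulative log-odds that the sponsor used are not reported, so this is a separate question and nothing below rests on it.

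**2. Identifiability.** Add an error of variance v to the logit. With one rating per subject and period, averaging over the error shrinks all logits by about 1/√(1+0.346v). Multiplying the cutpoints and effects by √(1+0.346v) therefore restores almost the same likelihood. For v=4: √2.384=1.544; ln(1.27)×1.544=0.369; OR≈1.45. Numerically, v from 0.5 to 4 changes the expected deviance at N=110 by only 0.002–0.012, while the fitted lens OR moves from 1.27 to 1.30–1.46. A 3×3 UN matrix has six parameters, and the data inform essentially three of them, the between-period correlations.

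**3. If the subject link is lost.** Simulation, 1,500 runs per row: three categories, exact marginal proportional odds, Gaussian-copula correlation, and sequence, period, lens and carryover fitted. True OR 1.27:

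| N | Correlation | Independence SE | True SD | SE too large by | Power, independence | Power, subject-clustered |
|---|---|---|---|---|---|---|
| 83 | 0.3 | 0.273 | 0.248 | 10% | 50% | 62% |
| 83 | 0.5 | 0.272 | 0.219 | 24% | 49% | 72% |
| 83 | 0.7 | 0.272 | 0.187 | 46% | 49% | 88% |
| 110 | 0.3 | 0.236 | 0.211 | 11% | 65% | 74% |
| 110 | 0.5 | 0.236 | 0.195 | 21% | 67% | 85% |
| 110 | 0.7 | 0.236 | 0.165 | 43% | 71% | 95% |

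Hand check at N=110, correlation 0.5, using power ≈ Φ((0.6395−2.393×SE used)/true SD). Independence: (0.6395−0.5640)/0.1953=0.39, or 65%. Clustered, with SE 0.188: (0.6395−0.4499)/0.1953=0.97, or 83%. Repeat simulations at N=110 stayed within 64–71% (independence) and 74–96% (clustered). At N=83 and correlation 0.5, splits of 0.35/0.07 and 0.21/0.21 gave an SE 21–24% too large.

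**4. Direction of the error.** At a true OR of 0.67 and N=83, the independence fit declared non-inferiority in 0.4%, 0.07% and 0% of runs, against 0.83% nominal.

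**5. Scale of the margin.** A fall from 0.58 to 0.481 in the population rate is a marginal OR of 0.67. Under a normal subject intercept, the same fall is a subject-specific OR of 0.62, 0.57 or 0.52 for SD 1.0, 1.5 or 2.0 (numerical integration). The approximation 0.67^√(1+0.346·SD²) gives 0.63, 0.59 and 0.54. The SDs are assumed.

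**The case against.** The strongest reply is that Plan B does address dependence. It names errors within a subject across periods and gives them the most general covariance, of which a subject intercept is a special case. Only the diagonal is unidentified, and the correlations are estimable once the model is rewritten. That stands, so it would be too strong to say that Plan B ignores the subject or that nothing in its matrix can be estimated.

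A reader might also infer that Plan B falls back to independence, because Plan A's contingency and the planning model both name variance components. The documents do not say so. Plan A's sentence is conditional, belongs to Plan A and concerns a different matrix, and section 14.2 describes a planning calculation. Independence is a possible outcome of fitting, not a rule of the plan.

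Nor do the documents support a worry about false non-inferiority: positive correlation ignored here makes the interval too wide, so the risk is the sponsor's.

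Finally, the stand-alone SAP may supply the missing form. That limits confidence. But section 14.10 commits the analysis to the methods as set out in the protocol, and that text cannot be run as written.

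**Conclusion.** The point holds as a specification gap. The sole model for the distance test gives no estimable link between a subject's three ratings, no subject effect and no fallback. The other items share the gap whenever their association test sends them to Plan B.

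If the link is lost, the distance SE is about 10–46% too large over the two sample sizes examined. Power at N=110 is then about 64–71% instead of about 74–96%. The existence of the gap follows from the text. Its size rests on the assumed correlations and category split, on zero site variance, and on the planning OR of 1.27 being marginal. If the between-period correlations were small, the loss would be small.

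**What to change.** In Plan B, replace the sentence on residual errors with an estimable subject link, keeping sequence, period, lens, carryover and site. Either of these will do:

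- a marginal cumulative-logit model with empirical standard errors clustered on subject; or
- subject nested within site as a random effect, as Plan A already has.

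Also:

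- State a fallback for non-convergence that keeps the subject link.
- State whether 0.67 is a marginal or a subject-specific odds ratio. The marginal model fits the margin's derivation from a population rate of 0.58. With a random intercept, the same 10 points corresponds to roughly 0.52–0.63 for subject SD 2.0–1.0 (assumed), so leaving 0.67 unchanged would be a stricter test.

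The cost is wording in the protocol or the stand-alone SAP before database lock. No new data or visits are needed.

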14.6. Secondary Analysis

Clarity of intermediate and near vision will be analyzed using the intent-to-treat population while clarity of distance vision will be analyzed using the per-protocol population.

Clarity of Distance Vision

Subjective responses to this item (defined as *aval*) will be categorized in the same manner as described for the primary endpoints. The outcome will be analyzed and using the model described for Primary Analysis Plan B above.

Hypothesis Testing

Non-inferiority of the Test compared to DT1MF will be conducted as follows:

Ho: $OR \le 0.67$ Ha: OR > 0.67

Where, the OR represents the odds of having a more positive experience (Excellent or Very Good) while wearing Test compared to DT1MF. Non-inferiority of Test relative to DT1MF will be concluded if the lower limit of the simultaneous 95% CI (98.33% individually) is above 0.67. A cumulative odds ratio margin of 0.67 was utilized as this corresponds to nomore than a 10% difference using a reference rate of 0.58 for DT1MF.

Clarity of Intermediate and Near Vision

Subjective responses to these two items (defined as *aval*) will be categorized in the same manner as described for the primary endpoints. Association between these two endpoints will be assessed using the same test as the primary endpoints and will following the same strategy.

Hypothesis Testing

Regardless of which Plan (Primary Analysis Plan A or B) is implemented, superiority testing will be conducted separately for clarity of intermediate and near vision as follows:

Ho: $OR \le 1$ Ha: OR > 1

Where, the OR represents the odds of having a more positive experience (Excellent or Very Good) while wearing Test compared to DT1MF. Superiority of Test relative to DT1MF will be concluded if a lower limit of a simultaneous 95% CI (98.33% individually) is above 1.

14.7. Other Exploratory Analysis

If co-primary and all secondary hypotheses are met, then a meta-analysis will be performed on the following exploratory items utilizing data from all historical studies with database hard-

lock (completed after design-lock [Phase 2b]. This will include , , , , , and (if database is hard-locked at the time this analysis is performed). The approximate number of subjects expected from the historical data is 300. The approximate allocation of subjects by study is displayed in Table 9 below.

Table 9 Clinical Studies Planned to be Utilized in Exploratory Meta-Analysis

Study Number	Population Included	Approximate Allocation of Subjects	
	Hyperopes	75	
	Myopes	78	
	Hyperopes	60	
	Hyperopes and Myopes	100	

is currently in execution; will begin January 2022

Any analyses performed on exploratory endpoints will be on the intent-to-treat population. Statistical analysis will follow the Meta-Analysis approach as discussed in Whitehead ²⁰ This analysis will be discussed completely in the stand-alone SAP.

The stand-alone SAP will include full details describing the following:

- 1. Historical data to be utilized
- 2. Methodology for assessing associations between endpoints within a grouping
- 3. Model details to be utilized for each grouping
- 4. Strategy for adjustments for multiple testing
- 5. Strategies regarding utilizing subject data, if a subject participate in more than 1 historical study
- 6. Methodology for accounting for different study designs

